## **Introduction**

Mental health disorders are among the leading causes of the global health-related burden. Mental health disorders are exacerbated by poverty and exposure to adversity such as conflict and negative shocks. The Global Burden of Disease Study (2020) showed that the two most disabling mental health disorders were depressive and anxiety disorders. Both ranked among the top 25 leading causes of burden worldwide in 2019, with an estimated 3 to 4 percent of the global population suffering from each (Abbaftati et al. 2020). Among conflict-affected populations, estimated prevalence of mental disorders rises to 22.1 percent (Charlson et al. 2019). Despite the high prevalence, adequate care for mental illness is mainly inaccessible in low and middle-income countries. The treatment gap (the percentage of individuals who require care but do not receive the treatment) is estimated at 80% (Ridley et al. 2020).

Recent work in economics and psychology suggests that poverty and low psychological well-being may mutually reinforce each other. For example, poverty may lead to stress, which can cause mental health challenges (Chemin, De Laat, and Haushofer 2013; Hammen 2005). Conversely, mental health challenges may affect labor market participation and productivity and thus may exacerbate poverty (Haushofer and Fehr 2014; Ridley et al. 2020). This potential feedback loop suggests that interventions that alleviate poverty may effectively reduce poverty and improve mental health. Similarly, interventions targeting mental health may improve mental health and poverty. Alternatively, if mental health and poverty are strong complements, interventions that address both poverty and mental health jointly may be most effective in improving both outcomes (Elliott, 2016, Lund, 2012).

The widespread incidence of common mental health disorders calls for psychotherapy models that may be more scalable and flexible to address multiple mental health-related problems. Given the bidirectional link between poverty and mental health and the limited mental health treatment in many low income settings, combining antipoverty interventions with psychotherapy delivered by non-specialists may be promising (Ridley et al. 2020). Using a randomized control trial design (RCT), this study will compare the impact of a psychotherapy program with and without a one-time lump sum cash transfer on measures of both economic and psychological well-being outcomes.

## **Objective**

### ***General Objective***

The study's objective is to estimate the impact of group Problem Management plus (GPM+), with and without a lump-sum cash transfer, on mental health, daily activities, and economic outcomes among Productive Safety Net Program (PSNP) clients in the regions of Amhara and Oromia.

### ***Research questions***

The specific research questions to be answered are:

- 1) What is the impact of gPM+ on PSNP clients' mental health and daily activities immediately after gPM+ sessions end?;
- 2) What is the impact of gPM+ on PSNP clients' mental health, daily activities, and economic well-being 1-year after gPM+ sessions end?
- 3) What is the impact of a one-time lump-sum cash transfer on mental health, daily activities, and economic well-being 1-year after gPM+ sessions end?;
- 4) What is the added impact of combining gPM+ with a one-time lump sum cash transfer one year after gPM+ sessions end?

## **Background**

### ***Study setting***

Since its inception in 2005, PSNP has been a cornerstone of the Ethiopian government's strategy for poverty alleviation, disaster risk management, and rural development. The PSNP provides food or cash transfers targeted to poor households through payments for seasonal labor on public works or direct support to families whose primary income earners are elderly or disabled. With more than 8 million beneficiaries, the PSNP is one of Sub-Saharan Africa's most prominent social protection programs. The PSNP has played an essential role in improving the lives of poor Ethiopian households by reducing household food insecurity, increasing asset holdings, and improving agricultural productivity (Berhane et al. 2014; Hoddinott et al. 2017).

The Strengthen PSNP5 Institutions and Resilience (SPIR II) Resilience Food Security Activity (RFSA) in Ethiopia is a five-year project (2021-2026). This is a graduation model social protection program that supports the implementation of the fifth phase of the Productive Safety Net Program (PSNP5) in the Amhara and Oromia regions and provides complementary livelihood, nutrition,

gender, and climate resilience activities to strengthen the program and expand its impacts. World Vision leads the implementation of the SPIR RFSA which will serve nearly 500,000 PNSP clients in Ethiopia's most vulnerable woredas in Amhara and Oromia regions. As part of its activities, World Vision and implementing partners will implement the gPM+ and cash transfer interventions.

This study will be conducted in 70 kebeles from 13 Woredas across the Oromia (5 Woredas) and Amhara (8 Woredas) regions of previous SPIR I study sites. Many adverse events have affected these kebeles, including political conflict, COVID-19, fall armyworm, and desert locust infestations. The proportion of fall army-worm and desert locust-affected households is higher in Oromia than in Amhara, with 35 (Amhara) and 65 percent (Oromia) of households reporting crop loss due to either desert locust or fall army-worms (Alderman et al. 2021). Even before the recent conflict, which has affected large parts of the country, a phone survey conducted during COVID-19 (June 2020) among SPIR I households found high levels of self-reported stress, with about 35% of respondents in Amhara and 85% in Oromia reporting being extremely stressed (Alderman et al. 2020). Depressive symptoms were also high among men and women in SPIR I study areas, with approximately 24-28 percent of males and females revealing mild-to-severe levels of depressive symptoms (PHQ-9 $\geq$ 5) and 4.6–6.2 percent moderate-to-severe levels (PHQ-9 $\geq$ 10) of depressive symptoms (Alderman et al. 2021). The mild-to-severe rates are slightly higher than the 22% prevalence rate of common mental illness reported in a systematic review of the general Ethiopian population (Kassa and Abajobir 2018).

While mild to severe depression is common in these study sites, treatment is limited. Most psychiatric services are concentrated in Addis Ababa, although the National Mental Health Strategy developed in 2012 aims to decentralize and integrate mental health services into primary health care (Hanlon et al. 2019; Negash et al. 2020).

### ***Interventions***

Problem Management Plus (PM+) is an intervention developed by WHO in 2013 to address common mental health problems such as depression, stress, and anxiety. It involves problem management (PM) plus (+) selected behavioral strategies to address both psychological issues (e.g., stress, fear, feelings of helplessness) and practical problems (e.g., livelihood problems,

---

 Amhara: Sekota; Gazgibla; Dahina; Bugna; Lasta; Gazo; Wadla; Meket. Oromia: Girawa; Kurfachele; Gemechis; Darolebu; Chiro

conflict in the family) (World Health Organization 2016). It was conceived initially as individual counselling composed of 5 sessions. It has been adapted to a group intervention (gPM+), with studies in Nepal and Pakistan demonstrating its effectiveness and feasibility (Rahman et al. 2019; Jordans et al. 2021). It is an intervention designed to be scalable and implemented by non-specialists following brief training. World Vision will adapt the gPM+ materials to the local context in Amhara and Oromia study regions.

In villages randomized to the gPM+ treatment, same-sex therapy groups of 3 to 8 individuals will be formed and facilitated by Community Health Facilitators (CHF) for women and Men's Group Facilitators (MGF) for men. Most CHF and MGF have experience facilitating prior mental health interventions, including interpersonal psychotherapy group (IPT-G) in SPIR I, and will receive a 9-day training related to gPM+. The gPM+ intervention consists of five, 90-minute group sessions which will be delivered weekly over five weeks by the trained CHF and MGF.

Eligible households in villages randomized to the Cash treatment will also receive a one-time lump sum transfer worth the equivalent value in Birr of \$300 USD. While the transfer is unconditional, it will be presented as a 'livelihoods transfer' to support income-generating activities that improve livelihoods. The transfer will be at the household level, so the total amount is the same regardless of whether one or two individuals per household participate in the study. The transfer will be timed to be distributed one to two months after the last gPM+ session.

## **Study design**

The impact of gPM+ will be assessed through a two-stage cluster randomized control trial (cRCT) design. In the first stage, 70 kebeles will be randomized to receive cash or no cash. Randomization of the cash treatment is at the kebele level in order to reduce the risk of spillovers, contamination, and resentment. Randomization of kebeles will be stratified by woreda. In the second stage, within each kebele, up to 6 villages will then be randomized to receive either gPM+ or not receive it, leading to the following four intervention arms across 252 villages:

- Arm-1: control
- Arm-2: gPM+ only

---

[figure not shown]
 Group size will depend on how many individuals are screened in per village

 Although most kebeles have between 3-5 villages, the exact number of villages per kebele varies.

- Arm-3: lump-sum cash transfer only
- Arm-4: lump-sum cash transfer and gPM+.

Study participants in all intervention arms will receive information on locally available mental health services and be PSNP public works clients. Arm 2 will additionally provide study participants with the gPM+ therapy, Arm 3 will additionally provide a one-time lump sum cash transfer, and Arm 4 will provide both the gPM+ and cash transfer.

[figure not shown]
The evaluation will include a baseline survey conducted before implementing the gPM+ or cash transfer intervention (July-August 2022, see Figure 1). The endline survey will be conducted on the same individuals right after the gPM+ intervention but before the cash is rolled out (September-October 2022). A one-year post-intervention survey will be conducted approximately one year after the end-line, approximately one year after the gPM+ sessions and 9 months after the cash transfer (September-October 2023).

### ***Randomization***

Randomization was conducted in STATA by the research team using the randtreat command. First, 70 kebeles were stratified by woreda, and randomized to either the Cash or No-Cash treatment. Second, 252 villages were stratified by kebele and randomized to either receive or not receive the gPM+ intervention. At each stage, misfits were randomly assigned within each strata, leading to slightly unequal number of villages per treatment arm (See figure 1).

**Figure 1: Study design**

### ***Study population***

The population for this study are individuals residing in Amhara and Oromia and registered and assisted by PSNP public works program. Moreover, to be eligible, individuals must have signs and symptoms of depression or dysfunction, be between 18 and 59 years old, and be the main decision-maker or spouse of the main decisionmaker. The last criterion is added because we are interested in the relationship between mental health and economic decision-making, which is more relevant for the main household decision-makers. We allow both the primary decision-maker and spouse to be eligible because depression across spouses is often correlated, and therapy may be more beneficial when both are treated. Individuals will be excluded from the study if they present evidence of severe depression or suicide. A quick screening exercise will be conducted in the selected villages to identify eligible participants. The screening exercise will be based on the PSNP client list and include a brief survey that screens individuals for inclusion in the study (see section on “Screening survey” for more detail).

## **Sample and power calculations**

### ***Power calculations***

Power calculations for this study focused on a primary mental health outcome, PHQ-9, and economic outcome, the total value of productive assets. PHQ-9 is a widely used depression diagnostic instrument with scores that range from 0-27. For both outcomes, we drew on data from the endline SPIR I impact evaluation conducted in the same regions of Oromia and Amhara. Given

that SPIR I data did not have data on daily activities, we did not conduct power calculations on this outcome.

We power the study for estimating impacts 1-year after the gPM+ sessions ended across the 4 intervention groups as this requires the largest sample. Power calculations considered the study's design, adjusting for clustering and autocorrelation. Autocorrelations were estimated using the SPIR endline and midline data, while intra-cluster correlations (ICC) were assessed at the kebele level. Power calculations were conducted in STATA using `clustersampsi` command. The desired statistical power was set at 80%, and the desired significance level was set to 0.05. Given that the number of kebeles, villages, and gPM+ group size were pre-determined, we calculate the minimal detectable effect at 1 year post gPM+ for a given number of clusters and cluster size.

We set the number of villages to 252. The number of individuals per village will depend on the number of individuals screened into the study. The max gPM+ group size is 8 women and 8 men per village and the minimum is 3 women and 3 men. On average we expect about 12 individuals per village (6 men and 6 women) at baseline with a coefficient of variation of 0.25. Assuming 8% attrition, rounded to the nearest whole number, the number of individuals per village at 1 year post endline is 11, for a total of 2,772 individuals. For household level economic outcomes, the number of households is estimated differently as two individuals per household (main decision-maker and spouse) are eligible to participate in the study. We expect about 18 percent of the sample to be husband/wife pairs from the same household. This will reduce the number of observations for household-level economic outcomes to 2,218 households.

These parameters give us a minimal detectable effect (MDE) of 0.22 standard deviations on the PHQ-9 score and 0.25 standard deviations on the value of productive assets (Table 1), both which are considered small effect sizes. The MDE for the PHQ-9 is a lower bound effect size comparable to those found in Nepal and Pakistan (0.2-0.38 mean standardized difference for PHQ-9) 3-months after the gPM+ intervention (Jordans et al. 2021; Rahman et al. 2019).

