**Table 1: Minimal detectable effect for given sample at 1-year post-program data collection**

	MDE (SD)	ICC	Corr	K villages, per arm	N per cluster	N per arm	Total sample at 1 year post program
PHQ-9 score	0.22	0.13	0.29	63	11	693	2,772
Value of productive	0.25	0.16	0.23	63	9	567	2,268

assets							
--------	--	--	--	--	--	--	--

\*2nd stage comparison of villages across the four different treatment arms

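### Table 1's minimal detectable effects suit the village-randomised gPM+ comparison but not the kebele-randomised cash comparison, and the interaction has none

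*Combined protocol and SAP*

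**What the plan says.** Under Study design and Randomization, the combined protocol and SAP describes two stages. Cash is allocated to 70 kebeles within woreda strata; gPM+ is then allocated to 252 villages within kebele strata. Research questions 2, 3 and 4 ask about gPM+, cash and their combination at one year. In EQ 2 (Empirical approach) these are beta2, beta1 and beta3.

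Power calculations sets the target: "The desired statistical power was set at 80%, and the desired significance level was set to 0.05". It says that "intra-cluster correlations (ICC) were assessed at the kebele level", and it presents the calculation as covering the one-year comparison of all four groups: "We power the study for estimating impacts 1-year after the gPM+ sessions ended across the 4 intervention groups as this requires the largest sample". The result is one MDE per outcome: "minimal detectable effect (MDE) of 0.22 standard deviations on the PHQ-9 score and 0.25 standard deviations on the value of productive assets".

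The two rows of Table 1 (MDE, ICC, correlation, villages per arm, n per cluster, n per arm, total) read "PHQ-9 score 0.22 0.13 0.29 63 11 693 2,772" and "Value of productive 0.25 0.16 0.23 63 9 567 2,268". The footnote describes a second "stage comparison of villages across the four different treatment arms". There is no separate MDE for cash or for the interaction.

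**The concern.** Table 1 counts 63 clusters in every arm, but the cash arms are formed by randomising kebeles, about 35 in each. All villages in a kebele share one cash allocation. Whatever correlation lies between kebeles therefore acts on larger and fewer clusters than the table assumes, and the plan says its ICC was assessed at exactly that level.

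At stake is the reading of research question 3, including productive assets, the economic outcome chosen for the power case. If the true MDE for cash is larger than stated, a null result could be taken as evidence against a 0.22-0.25 SD effect that the trial had less than 80% power to detect. Research question 4 has no stated power, so a null interaction has no benchmark.

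**Working it through.** **Inputs.** Power calculations and Table 1 give:
- PHQ-9: ICC 0.13, correlation r = 0.29, m = 11 per village, N = 693 per arm.
- Assets: ICC 0.16, r = 0.23, m = 9, N = 567.
- CV of village size 0.25; alpha 0.05; power 80%.

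Two-sided testing is assumed, so the multiplier is 1.960 + 0.842 = 2.802.

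**1. Reproduce Table 1.** MDE = 2.802 × sqrt(2 × DE × (1 − r²) / N), with DE = 1 + ((1 + CV²)m − 1) × ICC.
- PHQ-9: DE = 1 + (1.0625 × 11 − 1) × 0.13 = 2.389; MDE = 2.802 × sqrt(2 × 2.389 × 0.9159 / 693) = 0.2226.
- Assets: DE = 1 + (1.0625 × 9 − 1) × 0.16 = 2.370; MDE = 2.802 × sqrt(2 × 2.370 × 0.9471 / 567) = 0.2493.

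These match 0.22 and 0.25, so the table's model is 63 independent villages per arm. The text gives 2,218 households where the table gives 2,268; using 2,218 changes the assets MDE only to 0.250.

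**2. Cash against control, ICC at kebele level.** Villages per kebele: 252/70 = 3.6, or about 1.8 per gPM+ condition. Assuming a 35/35 split and equal kebele sizes, each kebele contributes 1.8 × 11 = 19.8 people or 1.8 × 9 = 16.2 households to the contrast.
- PHQ-9: DE = 1 + (1.0625 × 19.8 − 1) × 0.13 = 3.605; MDE = 0.273. Power at 0.22: standard error 0.273/2.802 = 0.0976; 0.22/0.0976 − 1.96 = 0.29, giving 62%.
- Assets: DE = 1 + (1.0625 × 16.2 − 1) × 0.16 = 3.594; MDE = 0.307. Power at 0.25: 63%.

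The documents give no CV for kebele-level clusters. With CV 0 the MDEs are 0.267 and 0.300, and power is 64% and 65%. Simulating 70 kebeles and 252 villages gave 0.268 and 0.302.

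**3. Vary the split of the ICC.** Let a be the kebele variance, b the village-within-kebele variance, e the residual, k = 1 + CV² and f = 1 − r². The contrast variances are:
- cash: 2f(ka/35 + kb/63 + e/N)
- gPM+: 2f(kb/63 + e/N)
- interaction: 4f(kb/63 + e/N)

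The kebele term drops out of the last two because both are contrasts within kebeles. Ranges below are for CV 0 to 0.25.

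| ICC assumption | Cash MDE, PHQ-9 / assets | Power for cash at 0.22 / 0.25 | gPM+ MDE | Interaction MDE |
|---|---|---|---|---|
| All between kebeles | 0.267-0.273 / 0.300-0.307 | 62-64% / 63-65% | 0.13 / 0.15 | 0.19 / 0.21 |
| Half kebele, half village | 0.244-0.249 / 0.274-0.280 | 70-71% / 71-73% | 0.18 / 0.20-0.21 | 0.26 / 0.29 |
| None between kebeles | 0.218-0.223 / 0.245-0.249 | 79-81% / 80-82% | 0.22 / 0.24-0.25 | 0.31 / 0.35 |
| Woreda effects absorb half, rest between kebeles | 0.212-0.219 / 0.237-0.245 | 80% or more | 0.13-0.14 / 0.15-0.16 | 0.19-0.20 / 0.21-0.22 |

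In the simulation with all the ICC between kebeles, the interaction MDE was 0.198 and 0.229, close to the first row.

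**The case against.** Three defences deserve weight.

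**The footnote.** It labels Table 1 a second-stage comparison, which is the gPM+ stage. That is partial disclosure. But it extends the comparison to all four arms, which includes cash against no cash, and the text states the MDEs without limit.

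**Woreda.** Kebeles are stratified by woreda and EQ 2 carries woreda fixed effects. If these absorb half the ICC, the stated MDEs hold for cash. This stands as a possibility, but the documents do not say whether the SPIR I ICC is net of woreda. It makes the conclusion conditional without removing it.

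**gPM+.** Table 1 is sound or conservative for this contrast, and the only external benchmark offered for the PHQ-9 MDE comes from gPM+ trials. This stands in full.

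A reader might also draw two stronger conclusions that the documents do not support. One is that the interaction must have an MDE of 0.31 / 0.35 SD and only about 50% power at the stated values. Those figures assume no kebele-level correlation, whereas 0.27 / 0.31 for cash assumes it is all there; both cannot hold in one trial. Under the cash premise the interaction MDE falls below Table 1. The other is that the sentence about requiring the largest sample is false. It does not claim that a pairwise contrast needs more than the interaction. Its natural comparator is the endline analysis, which pools arms 1 and 3 against arms 2 and 4, and on that reading it is correct.

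**Conclusion.** The point holds in conditional form. Table 1's arithmetic is right, but it is applied to a contrast that its model does not describe. Taking the ICC at kebele level, as the plan states, the cash MDE is about 0.27 SD (PHQ-9) and 0.30-0.31 SD (assets). Power at the stated MDEs is about 62-65%, some 15 to 18 points short of 80%. This rests on an assumed 35/35 split, equal kebele sizes and two-sided testing. If half the ICC is between villages within kebeles, the cash MDE is about 0.24-0.25 / 0.27-0.28; if woreda effects absorb half, it is about 0.21-0.22 / 0.24-0.25 and there is no shortfall. The documents give neither split.

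For gPM+ the stated figures are adequate or conservative (about 0.13-0.22 / 0.15-0.25). For the interaction the firm finding is only that no MDE is stated; it could lie anywhere from about 0.19-0.20 / 0.21-0.22 to 0.31 / 0.35. It would go too far to say that the design cannot deliver the stated MDEs for cash, or that the trial as a whole is underpowered.

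**What to change.** Replace Table 1 with one row per contrast: gPM+, cash and interaction. Compute all three from a single split of the SPIR I ICC into kebele and village-within-kebele parts, net of woreda, and state that split. Use about 35 kebeles per arm for cash. Restate the cash MDE as about 0.27 SD (PHQ-9) and 0.31 SD (assets) unless a woreda-adjusted ICC supports a smaller value. In the text of Power calculations, limit the 0.22 / 0.25 claim to the gPM+ comparison. Keep the sentence on the largest sample, but say which analyses it compares.

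The cost is a re-estimate of the ICC from data the team already used, one table and a few sentences. Sample, allocation and fieldwork do not change. The drawback is a probably less favourable stated figure for cash; the gPM+ figure may improve.

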**Table 1: Minimal detectable effect for given sample at 1-year post-program data collection**

	MDE (SD)	ICC	Corr	K villages, per arm	N per cluster	N per arm	Total sample at 1 year post program
PHQ-9 score	0.22	0.13	0.29	63	11	693	2,772
Value of productive	0.25	0.16	0.23	63	9	567	2,268

assets							
--------	--	--	--	--	--	--	--

\*2nd stage comparison of villages across the four different treatment arms

